1.3 Study summary

1.3.1 Overall study design and plan

This study is a prospective, multicenter, single arm design with a performance goal. All subjects will be evaluated at discharge, 7 days, 1, 3, 6 and 12 months following the index procedure. One early success interim analysis is planned for this study. Study population are patients aged 18-80 with symptomatic drug refractory PAF and indicated for catheter ablation.

A total of 123 non-roll-in subjects will be enrolled. Given at most 2 roll-in cases are planned for each investigator, a maximum of 147 subjects (including 123 non-roll-in and at most 24 roll-in subjects) will be enrolled in this study. All patients will be treated with BWI IRE system and then followed-up for 12 months.

1.3.2 Randomization and blinding

Not applicable.

Prior to locking the database for the planned effectiveness analysis, the study team will not conduct a summative analysis of the primary endpoint of long-term effectiveness. The results of interim analysis will be completed by a third-party independent statistician and reviewed by an independent Data Monitoring Committee (DMC). If the interim analysis does not show early success, the study team will remain blinded to the summary results of the primary endpoint of long-term effectiveness until the study is completed.

1.3.3 Sample size

The sample size of this study is determined by the primary effectiveness endpoint comparing to pre-specified performance goal (PG).

The PG for long-term effectiveness is 50%, based on the minimum acceptable

success rate for PAF at 12-month follow-up as recommended in the 2017 HRS/EHRA/ECAS/APHRS/SOLAECE Expert Consensus Statement on Catheter and Surgical Ablation of AF.

The hypothesis test for primary effectiveness endpoint is

- $H_0: P \leq 50\%$ vs.
- $H_1: P > 50\%$

Wherein, P is the true long-term effectiveness rate of the investigational device. To test the primary effectiveness rate is greater than the PG value of 50% with at least 80% power, a sample size of 110 evaluable non-roll-in subjects is required assuming the true primary effectiveness rate is 63%, with a one-sided significance level of 0.025, by using Normal Approximation method with Binomial Distribution (using Phat for estimating the variance) (PASS 15.0.5). Given the attrition rate of 10%, 123 non-roll-in subjects will be enrolled. Given at most 2 roll-in cases are planned for each site, a maximum of 147 subjects (including both non-roll-in and roll-in subjects) will be enrolled.

2 Basic considerations for statistical analysis

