7.1. Statistical design, method and analysis procedure

This study is a single-arm, prospective, multi-center clinical study with the prespecified performance goals.

The primary effectiveness endpoint is the long term effectiveness and will be evaluated on all non-roll-in subjects for whom receive ablation power. Group sequential design using the O'Brien and Fleming (OBF) sequential testing procedure with one interim analysis will be performed when 50% of treated patients with full 12-month follow-up data to claim early trial success. If early success is not achieved, a final analysis will be performed using all subjects' full follow-up data. The endpoint will be considered successful if the one-sided lower confidence bound based on Normal Approximation method with Binomial Distribution for its rate is greater than the PG value of 50%.

The safety endpoints will be evaluated on all subjects for whom have the catheter inserted or ablated with the IRE system. The number of events, the number and percentage of subjects experiencing any PAE, AE and serious AE will be summarized by using the terms of MedDRA.

CC1

[figure not shown]

CCI

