7.2.4. Significance level and power of clinical trial

For the primary endpoint, the one-sided significance level of 0.025 is used.

The power of this clinical study is around 80%.

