AEs will be summarized, including the number of AEs and the number and percentage of subjects experiencing any AEs. All PAE, SAEs and all procedure-/device-related AEs will be analyzed in same way. The severity, relationship, AE treatment intervention, seriousness and outcome of all AEs will be described.

In addition, all AEs, PAE, serious and non-serious AEs will be summarized according to the system organ classification and preferred terms of MedDRA, and a list will be generated, including but not limited to subject identification number, age, AE term, start and end time (corresponding duration post procedure), severity, relationship, AE treatment intervention, seriousness, and outcome.

Handling of missing value

Subjects will be contacted by different means, such as by telephone, to avoid missing value.

For the primary endpoint, missing primary endpoint data of the subjects in the FAS will be excluded from the final primary effectiveness analysis as described in “Primary analysis of primary endpoint” of Section 7.5.

For those who had the investigational device inserted but not ablated, they would be replaced, and new subjects should be screened and enrolled to ensure total 110 evaluable non-roll-in subjects.

For baseline information, operational information, or secondary endpoints, all observed data will be used for analysis. Missing data imputation will not be

performed.

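### SAP 1.3.3 gives 80% as a minimum power at 110 evaluable subjects; that is right by its normal approximation (80.6%), but the protocol's success rule has exact power of about 77.5% at that size

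*SAP*

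**What the plan says.** SAP 1.3.3 sets the performance goal ("The PG for long-term effectiveness is 50" per cent) and states that "with at least 80% power, a sample size of 110 evaluable non-roll-in subjects is required assuming the true primary effectiveness rate is 63" per cent, "with a one-sided significance level of 0.025". The same sentence gives the method: "by using Normal Approximation method with Binomial Distribution (using Phat for estimating the variance"), run in PASS. Attrition of 10% then takes 110 to 123 non-roll-in subjects.

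Protocol 7.2.4 is softer: "The power of this clinical study is around 80" per cent.

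Protocol 7.1 defines the decision: "The endpoint will be considered successful if the one-sided lower confidence bound based on Normal Approximation method with Binomial Distribution" exceeds the 50% goal. It adds an O'Brien-Fleming procedure "with one interim analysis will be performed when 50% of treated patients with full 12-month follow-up data to claim early trial success". The numerical boundary is not visible in the public text.

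Under Handling of missing value in protocol 7.5, "missing primary endpoint data of the subjects in the FAS will be excluded from the final primary effectiveness analysis". The number finally analysed is therefore not fixed in advance.

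**The concern.** The SAP words its power as a minimum. The calculation behind it treats the observed rate as continuous, whereas the trial is decided on a count. When the required count is rounded up to a whole number, true power can fall below the smooth figure, and the smooth figure here is only 0.6 points above 80%.

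The primary endpoint carries the trial's only confirmatory test, since the secondary endpoints are descriptive (protocol 7.5). SAP 3.2.1 says that an interim success would be used for product registration. At exactly 110 analysed subjects, the chance of missing a device whose true rate is 63% is 22.5%, where the SAP implies at most 20%.

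**Working it through.** **Inputs.** Goal 0.50, assumed true rate 0.63, one-sided alpha 0.025 (z = 1.96), 110 evaluable, 10% attrition: all from SAP 1.3.3. Success rule: protocol 7.1.

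**1. The plan's own figure.** Normal approximation with the variance at the estimated rate:

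- Power = Φ[(0.63 − 0.50)/√(0.63 × 0.37/110) − 1.96] = Φ(2.824 − 1.96) = Φ(0.864) = 80.6%.
- Required n = (1.96 + 0.8416)² × 0.63 × 0.37/0.13² = 108.3, so 110 is enough.
- 110/0.9 = 122.2, rounded up to 123.

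All three steps reproduce.

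**2. The count that the success rule needs at 110.** Lower bound = p̂ − 1.96 × √(p̂(1 − p̂)/110).

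- 65 successes: p̂ = 0.5909, bound = 0.4990, which fails.
- 66 successes: p̂ = 0.6000, bound = 0.5085, which passes.

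The cut-off is 66. It stays at 66 with critical values of 1.969 or 1.977, with the variance taken at 50%, and with an exact binomial test.

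**3. Exact power at 110.** P(X ≥ 66 | n = 110, p = 0.63) = 0.7746. The chance of a miss is 1 − 0.7746 = 22.5%. Solving P(X ≥ 66 | n = 110, p) = 0.80 gives p = 0.634.

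**4. With an interim look (assumed boundaries).** Two O'Brien-Fleming-type pairs were tried, z = 2.963/1.969 and z = 2.797/1.977, with the look at 55 of 110 and the rule of step 2 at both looks. Both pairs give cut-offs of 38/55 and 66/110. Power = P(X₁ ≥ 38) + P(X₁ < 38 and X ≥ 66) = 0.7774. Moving the look to 61 or 62 subjects, or using the variance under 50%, keeps power between 77.5% and 77.9%.

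**5. Other analysed sizes.** Exact single-look power at 63%, same rule:

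| n | Cut-off | Power |
|---|---|---|
| 108 | 65 | 76.1% |
| 109 | 65 | 79.7% |
| 110 | 66 | 77.5% |
| 111 | 66 | 80.9% |
| 112 | 67 | 78.7% |
| 113 | 67 | 82.0% |
| 114 | 68 | 79.97% |
| 115 | 68 | 83.1% |
| 116 | 69 | 81.1% |
| 117 | 69 | 84.1% |
| 118 | 70 | 82.2% |
| 119 | 71 | 80.3% |
| 120 | 71 | 83.3% |
| 121 | 72 | 81.4% |
| 122 | 72 | 84.3% |
| 123 | 73 | 82.5% |

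From 110 to 123, power is below 80% at three of the 14 sizes, and the unweighted mean is 81.5%. Just below 110 it is mostly under 80%: 107 gives 78.4% and 105 gives 77.1%, while 106 gives 80.6%.

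**The case against.** The best defence is that the sentence is correct as written. It names its method, and by that method 80% is exceeded. Normal-approximation power is common practice, and anyone who reruns the software will get the same answer. This stands as to the arithmetic. It does not make the minimum true of the rule that decides the trial.

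The second defence is that 110 is the lowest point of a saw-tooth over 110 to 123. One more subject gives 80.9%, and a true rate of 63.4% instead of 63% closes the gap; the 63% is itself less certain than that. This also stands, and it limits the size of the point. But 110 is the number the SAP chose to attach its minimum to.

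Three stronger readings are tempting, and the documents do not support them:

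- *The sample size was miscalculated, or the trial is materially underpowered.* The calculation reproduces, and exact power is 82.5% if all 123 are analysed. Averaging over binomial 10% attrition from 123 (an assumption) gives 79.6%, but about 35% of that weight lies below 110. Restricted to 110 or more, the same average is 80.3%.
- *The SAP hides the dependence of power on the number with endpoint data.* SAP 1.3.3 ties power to evaluable subjects and inflates for attrition. Related sections, such as protocol 7.2.1 and 7.3 and SAP 4.1, are blacked out and may say more.
- *The type I error is inflated.* The actual interim boundary is not visible, so no such conclusion can be drawn. It is also a separate question from power.

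**Conclusion.** The point holds as a minor one. The minimum of 80% in SAP 1.3.3 is met by the approximation it names (80.6%) but not by the protocol 7.1 rule at 110 subjects, where exact power is 77.5% for a single look and about 77.7% with a look at 55 under either assumed boundary. The shortfall is about 2.5 points and disappears at many nearby sizes.

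The single-look figure rests only on the stated goal, rate, alpha and rule. The two-look figure also rests on the assumed boundaries and timing; no variant tried reached 80% at 110. The wording in protocol 7.2.4 is fair, since 77.5% and 82.5% both fit it.

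**What to change.** In SAP 1.3.3, replace the phrase that gives 80% as a minimum by a statement that power at 110 evaluable subjects is 80.6% by the normal approximation and about 77.5% by the exact binomial for a single look, with 82.5% at 123. Alternatively, adopt the approximate wording of protocol 7.2.4 and give these exact figures beside it. The sponsor, who holds the interim boundary, should recompute the exact figures with it.

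Protocol 7.2.4 can stay as it is. The cost is one reworded sentence and a short calculation: no added subjects, no change to the success rule or the sample size, and no trial data needed.

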2.1 General rules

All statistical analyses will be performed based on SAS® 9.4 M6 version.

Statistical analysis will be performed mainly using descriptive statistics. The number of cases, mean, standard deviation (SD), median (first quartile Q1, third quartile Q3), minimum and maximum will be used for continuous variables; and the number of cases and percentage will be calculated for categorical variables. The number of missing will not be included in the denominator for percentage calculation. Table 1 shows the number of decimal places retained for statistical parameters.

Table 1. Number of decimal places retained for statistical parameters

| Statistical magnitude | Number of decimal places retained |
|-----------------------|-------------------------------------------------------------------------------------------------------------------------------------|
| Mean, Median, Q1, Q3 | Retain 1 more decimal place than the original data, up to a maximum of 4 decimal places. |
| SD, 95% CI | Retain 2 more decimal place than the original data, up to a maximum of 4 decimal places. |
| Maximum, Minimum | Retain the same number of decimal places as the original data, up to a maximum of 4 decimal places. |
| Percentage | Retain one decimal place; if the percentage reaches 100%, it is expressed as “100”, if the percentage is 0, it is expressed as “0”. |
| P value | Retain 4 decimal places; when all 4 decimal places are 0, it is expressed as $P < 0.0001$ |

2.2 Definition of analysis set

Enrolled subject set: It refers to all patients who have signed ICFs, meet all

eligibility criteria in screening period, and have been successfully enrolled.

CCI

A large rectangular area of the page is completely blacked out, representing redacted content. The text 'CCI' is printed in red at the top left corner of this redacted area.

2.3 Rules for data processing

2.3.1 Definition of baseline

Unless otherwise specified, baseline for this study is defined as the result of the last non-missing assessment/examination prior to the start of the index ablation procedure. If a specific time point is not collected, the assessment/examination on the day of procedure is considered to be performed prior to treatment.

2.3.2 Definition of study day

The study day, with the day of index ablation procedure as the reference, is defined as the time interval between the date of event/assessment and the date of index ablation procedure. The day of the index ablation procedure is designated as Day 0 of the study.

Study Day = Date of event/assessment – Date of index ablation procedure

2.3.3 Study periods

The study is divided into a blanking period and an effectiveness evaluation period after the index ablation procedure.

- Blanking period: 1-90 days following the index ablation procedure.
- Effectiveness evaluation period: 91-365 days following the index ablation procedure. Since the visit window for each follow-up is specified in the protocol, i.e., the 12-month visit window is 335-395 days following the index ablation procedure, during the analysis, if a subject's 12-month visit

occurs after 365 days following the index ablation procedure and on or before the end of the protocol-defined 12-month visit window (i.e., ≤ 395 days), all observed failures will be considered as failures in the effectiveness evaluation period.

2.3.4 Definition of analysis window period

Visits during the study will be directly based on the visits recorded in the eCRF. Unless otherwise specified, the observed data will be summarized and analyzed per scheduled visits in the protocol.

All data collected, including data collected at scheduled visits and unscheduled visits, will be presented in the list.

2.3.5 Rules for missing data processing

In the final analysis, a sensitivity analysis for the primary endpoint, missing data will be imputed using multiple imputation.

No imputation will be performed for the missing data on baseline information, procedural information, or secondary effectiveness endpoints.

2.4 CCI

CCI

2.5 Subgroup analysis

Subgroup analyses will be performed for the primary endpoint in both FAS and SS after the primary endpoint success is achieved. Subgroup analyses will be performed on observed data only. The number of subjects in each subgroup, the number of subjects who achieved primary endpoint success, and the proportion will be presented, and logistic model will be used to calculate odds ratios and

their two-sided 95% CI among subgroups.

- Age (< 65 years, \geq 65 years)
- Gender (M, F)
- Baseline left atrium diameter (mm) ($>$ median, \leq median)
- Type of anesthesia during the index ablation procedure
- Activated clotting time (ACT) during index ablation procedure (sec) (<300 , [300, 350], ≥ 350)

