6.1.4.2. Exclusion criteria

1. AF secondary to electrolyte imbalance, thyroid disease, or reversible or non-cardiac cause (e.g., untreated documented obstructive sleep apnea and acute alcohol toxicity).
2. Previous LA ablation or surgery
3. Patients known to require ablation outside the PV region (atrioventricular reentrant tachycardia, atrioventricular nodal reentry tachycardia, atrial tachycardia, atrial flutter of unknown origin, ventricular tachycardia and Wolff-Parkinson-White).
4. Previously diagnosed with persistent AF (> 7 days in duration)
5. Severe dilatation of the LA (documented LAD >50mm antero-posterior diameter by Transthoracic Echocardiography (TTE) within 6 month prior to enrollment)
6. Documented left atrium (LA) thrombus within 48 hours prior to the index procedure by TEE or CT (in case of intolerance to TEE), or by ICE prior

to transeptal puncture during procedure

7. Documented severely compromised LVEF (LVEF <40%) by imaging within 6 months prior to enrollment
8. Uncontrolled heart failure or New York Heart Association (NYHA) Class III or IV
9. History of blood clotting, bleeding abnormalities or contraindication to anticoagulation (heparin, warfarin, or dabigatran)
10. History of a documented thromboembolic event (including TIA) within the past 12 months, or history of a documented left atrial appendage (LAA) thrombus
11. History of a documented symptomatic lacunar infarction within the past 12 months
12. Previous PCI/MI within the past 2 months
13. Coronary Artery Bypass Grafting (CABG) surgery within past 6 months
14. Valvular surgery, cardiac surgery (e.g. ventriculotomy, atriotomy) or valvular cardiac (surgical or percutaneous) procedure.
15. Unstable angina pectoris within the past 6 months
16. Anticipated cardiac transplantation, cardiac surgery or other major surgery within the next 12 months.
17. Significant pulmonary disease (e.g., restrictive pulmonary disease, constrictive or chronic obstructive pulmonary disease) or any other disease or malfunction of the lungs or respiratory system that produces severe chronic symptoms
18. Known significant PV anomaly that in the opinion of the investigator would preclude enrollment in this study
19. Has known pulmonary vein stenosis
20. Pre-existing hemi diaphragmatic paralysis
21. Acute illness, active systemic infection or sepsis

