3.1.6 Atrial fibrillation history

AF history of subjects will be summarized descriptively based on RI AS, FAS, and SS. The summary will be performed as follows:

- Duration of symptomatic PAF
Duration of symptomatic PAF (months) = (date of index ablation procedure - date of first symptomatic PAF episode) / 30.4375, wherein $30.4375 = (365*3+366)/(4*12)$.
- In the past 12 months, did the subject experience an episode of PAF
- Methods of identifying AF episodes
- Symptoms related to PAF episodes
- Number of episodes of PAF in the past 12 months
- Average duration of episodes in the past 12 months
- Average frequency of episodes in the past 12 months
- Arrhythmia type other than PAF
- Presence of ablation procedure history
- Number of previous ablation procedures, for subjects with arrhythmias treated by ablation in previous procedures
- Types of arrhythmias treated by ablation in previous procedures
- Time since last ablation (months) = (date of index ablation procedure - date of last ablation procedure) / 30.4375, wherein $30.4375 = (365*3+366)/(4*12)$.
- Technology used in the last ablation procedure

3.1.7 Assessment of left atrium (LA), left ventricular ejection fraction (LVEF), and pericardial effusion

Findings for baseline LA, LVEF and pericardial effusion will be summarized descriptively based on RI AS, FAS, and SS.

- Method of measurement
- LVEF (%)
- Left atrial diameter (mm)

- Left atrial volume (mL)
- Is any valvular regurgitation observed
 - If yes, valve type
 - Severity of regurgitation
- Pericardial fluid assessment
- Whether there is abnormal heart wall motion

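### In the visible text, SAP 2.5 relates left atrial diameter to success only through a split at the sample median, which gives up roughly a third of the information on that one descriptive association

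*SAP*

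**What the plan says.** SAP 2.5 plans subgroup analyses of the primary endpoint in both the FAS and the SS.

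- **Coding.** The item beginning "Baseline left atrium diameter (mm" has two categories, above the median and at or below it. No value in mm is given, so the median has to come from the trial's own data.
- **Method.** Each subgroup gets counts and proportions, and a "logistic model will be used to calculate odds ratios and" two-sided 95% confidence intervals. "Subgroup analyses will be performed on observed data only".
- **Condition.** The analyses are done "after the primary endpoint success is achieved".

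SAP 3.1.7 lists "Left atrial diameter (mm" among the baseline measurements summarised in the FAS and the SS. SAP 2.1 includes the median in the summary of every continuous variable. Protocol 6.1.4.2 excludes patients with "documented LAD >50mm antero-posterior diameter", so the upper end of the range is limited.

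No visible text puts diameter into an outcome model as a continuous term, and none plans subgroup tables for the case where the primary endpoint is not met. SAP 2.4, parts of SAP 3.2.1 and 4.1, and part of Protocol 7.5 are redacted.

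**The concern.** A measurement taken in mm is reduced to two groups before it is related to outcome. Subjects just above the median and subjects near the 50 mm limit count as the same, and subjects 1 mm apart on either side of the median count as different. The odds ratio is therefore less precise than the data allow, in a trial of about 110 evaluable subjects where any subgroup comparison is already weak.

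The cut also depends on the analysis set. If the FAS and SS medians differ, the same subject can be in the upper group in one table and the lower group in the other.

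The condition on success is a lesser matter. The visible text attaches no hypothesis or alpha to the subgroup odds ratios, so it is not clear that the condition protects an error rate. A prespecified look at the subgroups would be of interest after a disappointing result too. At stake is the quality of one descriptive comparison and the availability of a set of descriptive tables.

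**Working it through.** **1. The plan's own figures (SAP 1.3.3).** Inputs: "The PG for long-term effectiveness is 50" (per cent); "assuming the true primary effectiveness rate is 63" (per cent); one-sided alpha 0.025; power at least 80%; normal approximation with the variance from the estimated rate.

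- n = p1(1 − p1)(1.960 + 0.842)² / (p1 − p0)² = 0.63 × 0.37 × 7.849 / 0.13² = 108.3, so 109. The plan states 110, which agrees within two subjects.
- Power at 110: 0.13 / √(0.2331/110) − 1.960 = 0.864, which gives 80.6%.
- With 10% attrition: 110 / 0.90 = 122.2, so 123, as stated.

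The plan gives no figure for the information lost by the split.

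**2. Information kept by a median split.** For a linear association this is the squared correlation between X and the indicator that X exceeds its median. For a normal X the correlation is φ(0)/0.5 = 0.3989/0.5 = 0.798, and its square is 2/π = 0.637. The loss is 36.3%, and 110 × 0.637 = 70, so 110 subjects carry the information of about 70.

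**3. Sensitivity to the distribution.** The documents give no distribution for diameter, so these are assumptions.

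| Assumed diameter | Loss |
|---|---|
| Normal | 36% |
| Normal, mean 36-44 mm, SD 4-6 mm, truncated at 50 mm | 34-36% |
| Same, rounded to whole mm | 34-37% |
| Uniform | 25% |
| Lognormal (log-SD 0.15) | 38% |
| Logistic | 42% |
| Laplace | 50% |

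With rounding, ties at the median leave 45-49% of subjects in the upper group.

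**4. Logistic simulation.** n = 110, 63% success, normal covariate, linear logit, 3,000 replicates. The odds ratios per SD are illustrative. The middle columns give the chance that the 95% confidence interval excludes 1, used only as a scale for precision.

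| Odds ratio per SD | Continuous term | Median split | Loss of Wald information |
|---|---|---|---|
| 0.75 | 28% | 20% | 31% |
| 0.60 | 69% | 49% | 30% |
| 0.55 | 81% | 63% | 29% |
| 0.50 | 89% | 74% | 27% |

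A 55/55 split centred on 63% needs a difference of about 26 percentage points in success rate for 80% power. At 25 points the power is 78.3%, and at 26 points it is 81.5%.

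**5. How often the condition would withhold the tables.** These figures treat the final test as a single look at 110 subjects and ignore the redacted interim boundary.

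- True rate 63%, normal approximation: 1 − 0.806 = 19%.
- True rate 63%, exact binomial: the lower bound first exceeds 50% at 66 of 110, and the chance of fewer than 66 is 23%.
- True rate 60%, exact binomial: 46%.

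**The case against.** The strongest case on the other side is that this is one of five descriptive factors and nothing in the visible plan depends on it. If the table only shows consistency across subgroups, the chance that an interval excludes 1 is not its purpose. A two-group table is easy to read and needs no linearity assumption. All of this stands. It limits the importance of the point and is a reason to keep the split as a display. It does not explain why the more precise estimate, available from data already collected, should be left out.

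The redactions also count. The imputation model or another analysis in a redacted section could use diameter as continuous, so the point holds for the visible text only.

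Some stronger readings are tempting, and the documents do not support them.

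- A reader might infer that another trial could not reuse the cut. The median will be reported in mm through SAP 2.1 and 3.1.7, so it can be reused once known. It is simply not fixed in advance.
- A reader might picture very enlarged atria pooled with near-median ones. The 50 mm exclusion limits this: with the assumed means of 36-44 mm, eligible subjects lie at most about 6-14 mm above the centre.
- A reader might extend the argument to age. SAP 2.5 cuts age at a fixed 65 years, so the objection to a data-dependent cut does not apply there.
- A reader might infer that a failed trial would leave no subgroup information. SAP 2.3.4 lists all collected data and SAP 3.2.1.1 summarises the composite events for each subject. Only the planned subgroup tables would be missing, and later ones would be post hoc.

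On the condition itself, holding back subgroups after a failed primary test is a common safeguard against rescuing the trial through a favourable subgroup, and statisticians can reasonably differ. The wording may also concern timing, because SAP 1.3.2 and 3.2.1 keep the study team blinded to summary primary results if the interim does not show success. Even on that reading, the visible text makes no provision for a primary endpoint that is not met.

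**Conclusion.** The point holds as a low-cost improvement. In the visible text, left atrial diameter is related to the primary endpoint only through a split at the sample's own median, and the FAS and SS may use different cuts. The loss is about 27-37% of the information on this one association if diameter is roughly normal and the logit is linear, and 25-50% across the distribution shapes tried. The distribution and the effect sizes are assumptions, because the documents give neither. The sample size, the primary test and every visible decision rule are unaffected, and the comparison has limited power under either coding.

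The condition on primary success is secondary and is not an error. As written, it would withhold the planned tables in about one trial in five under the 63% assumption, or nearly half the time if the true rate were 60%, ignoring the interim boundary.

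**What to change.** In SAP 2.5, add to the same logistic analysis the odds ratio per 5 mm of baseline left atrial diameter as a continuous term, with its two-sided 95% confidence interval, in the FAS and the SS. Keep the median-split counts and proportions as a display. Both sets then report on the same scale even if their medians differ.

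The cost is a sentence in the SAP and a few output lines, with no new data, subjects or alpha. The small downside is a linearity assumption in about 110 subjects.

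As an optional change, the sponsor could state that the subgroup tables are produced whatever the primary result, are descriptive, and support no claim. Protocol 7.5 already treats the secondary endpoints as descriptive without multiplicity adjustment. If the sponsor prefers to keep the condition, the SAP should say whether it means only if the endpoint succeeds, or no earlier than that.
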